9. STATISTICAL CONSIDERATIONS

9.1. Statistical hypotheses (amended 16 December 2022)

Statistical hypotheses are associated to the confirmatory primary non-inferiority (NI) objectives, which will be tested sequentially to control overall Type I error.

Global type I error is controlled at 2.5% (1-sided).

The non-inferiority margins associated to each objective are provided in Table 15.

Table 15 Study objectives and null hypothesis

Objectives	Null hypothesis
Primary	

 To demonstrate the non-inferiority of RSVPreF3 OA investigational vaccine in terms of RSV-A neutralization antibodies when co-administered with the FLU vaccine compared to RSVPreF3 OA investigational vaccine administered alone. 	
 True Group GMT ratio between RSVPreF3 OA investigational vaccine (Control group) divided by RSVPreF3 OA investigational vaccine when co-administered with the FLU vaccine (Co-Ad group) in RSV-A neutralization antibody titers 1 month after the RSVPreF3 OA investigational vaccine dose is above 1.5.

 To demonstrate the non-inferiority of FLU vaccine when co-administered with the RSVPreF3 OA investigational vaccine compared to FLU vaccine administered alone. 	
 True Group GMT ratio between FLU vaccine (Control group) divided by RSVPreF3 OA investigational vaccine when co-administered with the FLU vaccine (Co-Ad group) in HI antibody titers for each of the FLU vaccine strains 1 month after the FLU vaccine is above 1.5.

 To demonstrate the non-inferiority of RSVPreF3 OA investigational vaccine in terms of RSV-B neutralization antibodies when co-administered with the FLU vaccine compared to RSVPreF3 OA investigational vaccine administered alone. 	
 True Group GMT ratio between RSVPreF3 OA investigational vaccine (Control group) divided by RSVPreF3 OA investigational vaccine when co-administered with the FLU vaccine (Co-Ad group) in RSV-B neutralization antibody titers 1 month after the RSVPreF3 OA investigational vaccine dose is above 1.5.

FLU vaccine is referring to FLU HD quadrivalent; HI: Hemagglutinin Inhibition; GMT: Geometric Mean Titer.

Statistical testing of each endpoint will be organized sequentially to control overall Type I error.

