2. STATISTICAL HYPOTHESES

The study includes the following confirmatory primary objectives.

- To demonstrate the non-inferiority of RSVPreF3 OA investigational vaccine when co-administered with the FLU vaccine compared to RSVPreF3 OA investigational vaccine administered alone in terms of RSV-A neutralization antibody GMT ratio at 1 month after the RSVPreF3 OA investigational vaccine dose (i.e. at Day 31[Visit 2] for the Co-Ad group and at Day 61[Visit 3] for the Control group).

Null hypothesis vs. Alternative hypothesis:

$$H_0: \mu_{\text{Control group}} / \mu_{\text{Co-Ad group}} > \log(1.5) \text{ vs. } H_a: \mu_{\text{Control group}} / \mu_{\text{Co-Ad group}} \leq \log(1.5)$$

where μ represents the expected mean of log transformed RSV-A neutralization antibody titers at 1 month after the RSVPreF3 OA investigational vaccine dose. The null hypothesis will be rejected if the upper limit of the two-sided 95% CI for the group GMT ratio (Control group divided by Co-Ad group) in RSV-A neutralization antibody titers 1 month after the RSVPreF3 OA investigational vaccine dose ≤ 1.5 .

- To demonstrate the non-inferiority of FLU vaccine when co-administered with the RSVPreF3 OA investigational vaccine compared to FLU vaccine administered alone

in terms of HI GMT ratio for each of the FLU vaccine strains at 1 month after the FLU vaccine (i.e. at Day 31[Visit 2] for both groups).

Null hypothesis vs. Alternative hypothesis:

$$H_0: \mu_{\text{Control group}}/\mu_{\text{Co-Ad group}} > \log(1.5) \text{ vs. } H_a: \mu_{\text{Control group}}/\mu_{\text{Co-Ad group}} \leq \log(1.5)$$

where μ represents the expected mean of log transformed HI antibody titers at 1 month after the FLU vaccine dose. The null hypothesis will be rejected if the upper limit of the two-sided 95% CI for the group GMT ratio (Control group divided by Co-Ad group) in HI antibody titers for each of the FLU vaccine strains 1 month after the FLU vaccine ≤ 1.5 .

- To demonstrate the non-inferiority of RSVPreF3 OA investigational vaccine when co-administered with the FLU vaccine compared to RSVPreF3 OA investigational vaccine administered alone in terms of RSV-B neutralization antibody GMT ratio at 1 month after the RSVPreF3 OA investigational vaccine dose (i.e. at Day 31[Visit 2] for the Co-Ad group and at Day 61[Visit 3] for the Control group).

Null hypothesis vs. Alternative hypothesis:

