2.1. Multiplicity Adjustment

Using a nominal alpha of 2.5% for each of them will ensure the global type I error for the primary objectives is controlled below 2.5%.

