4.2.2. Main analytical approach

The 2-sided 95% CI for group adjusted GMT ratio will be derived from an ANCOVA model* on \log_{10} transformed titer.

***Primary Analysis:** The model will include the treatment group and age category (age at vaccination: 65-69, 70-79 or ≥ 80 years) as fixed effects, and the pre-dose \log_{10} -transformed titer as covariate. Missing data will not be replaced. Titers below the assay cut-off will be replaced by half the assay cut-off, titers above the upper limit of quantification (ULOQ) will be replaced by the ULOQ.

Success criteria for non-inferiority and testing sequence:

The following testing sequence will be used:

1st sequence:

- The upper limit of the 2-sided 95% CI of the GMT ratio (Control group divided by Co-Ad group) for RSV-A neutralization antibodies is ≤ 1.5 .

AND

- The upper limit of the 2-sided 95% CI of the GMT ratio (Control group divided by Co-Ad group) for each of the FLU vaccine strains are ≤ 1.5 .

2nd sequence:

- The upper limit of the 2-sided 95% CI of the GMT ratio (Control group divided by Co-Ad group) for RSV-B neutralization antibodies is ≤ 1.5 .

Testing will progress in the 2nd sequence only if the 1st sequence is a success, so that no further adjustment of alpha is required.

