5. SAMPLE SIZE DETERMINATION

The target enrolment will be 1028 participants (514 in the group receiving the RSVPreF3 OA investigational vaccine co-administered with the FLU vaccine (Co-Ad group) and 514 in the Control group where RSVPreF3 OA investigational vaccine and FLU vaccine are administered staggered) to obtain at least 924 evaluable participants (462 in the Co-Ad group and 462 in Control group) for the evaluation of the primary objectives, assuming that approximately 10% of the enrolled participants will not be evaluable.

Each objective will be evaluated with a nominal type I error of 2.5%.

Table 2 Overall power to demonstrate primary objectives: non-inferiority of the immunogenicity of RSVPreF3 OA investigational vaccine when co-administered with FLU vaccine as compared to when administered alone- assuming 462 participants are available in each group

Endpoint	Standard deviation of log ₁₀ concentration	Reference ratio	Non-inferiority margin	Type II error	Power
RSV-A Non-inferiority* (1-sided test with alpha = 2.5%)					
GMTs RSV-A neutralization antibody	0.45	1.05	1.5	0.1%	99.9%
FLU Non-inferiority* (1-sided test with alpha=2.5%)					
GMTs HI H1N1 strain	0.6	1.05	1.5	2.5%	97.5%
GMTs HI H3N2 strain	0.6	1.05	1.5	2.5%	97.5%
GMTs HI B/Yamagata	0.6	1.05	1.5	2.5%	97.5%
GMTs HI B/Victoria strain	0.6	1.05	1.5	2.5%	97.5%
RSV-B Non-inferiority* (1-sided test with alpha = 2.5%)					
GMTs RSV-B neutralization antibody	0.45	1.05	1.5	0.1%	99.9%
Global Type II error to show non-inferiority					~10.0%
Global power					~90.0%

* Pass 2019 alpha = 2.5%, Two-Sample T-Tests for Non-Inferiority Assuming Equal Variance and Equal mean

For RSV: non-inferiority limit = 0.176 (=log₁₀[1.5]).

For each Flu vaccine strain: non-inferiority limit = 0.176 (=log₁₀[1.5]).

Reference Ratio= 0.0212 (=log₁₀[1.05])

Considering a slight interference of 1.05 in true GMTs in both groups with a common population standard error of 0.45 for the RSV-A and RSV-B neutralization antibodies and 0.6 for each of the FLU strains in log₁₀ transformed concentration, the study has at least 90.0% power to meet the primary objectives.

Nominal powers to evaluate secondary objective

The nominal power to evaluate the non-inferiority on seroconversion rate for each of the FLU strains is above 86%, depending on the plausible rates.

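### Joining RSV-A and all four FLU strains in one all-or-nothing first step makes the formal RSV-A claim depend on FLU; testing RSV-A first removes that dependence at no cost in alpha or in power elsewhere.

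*SAP*

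**What the plan says.** The objectives tables (Protocol Section 3, SAP 1.1) list three primary objectives, each to be demonstrated in its own right: RSV-A, FLU (four strains) and RSV-B. Footnotes send the reader to Protocol 9.4.1.1 and SAP 4.2.2 for the order of testing.

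Those two sections contain the same rule. The first sequence passes when the RSV-A upper limit AND the upper limits for all four FLU strains are at most 1.5. RSV-B forms the second sequence. "Testing will progress in the 2nd sequence only if the 1st sequence is a success, so that no further adjustment of alpha is required". No order is given inside the first sequence.

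Three other places bear on how this is read:

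- Protocol 9.1: "Statistical testing of each endpoint will be organized sequentially to control overall Type I error", with global error set at one-sided 2.5%.
- SAP 2, separately for each objective: "The null hypothesis will be rejected if the upper limit of the two-sided 95% CI for the group GMT ratio" is at or below 1.5. The RSV-A entry does not mention FLU.
- SAP 2.1, in full apart from the limit it names (below 2.5%): "Using a nominal alpha of 2.5% for each of them will ensure the global type I error for the primary objectives is controlled". It mentions neither the sequence nor an all-must-pass condition.

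**The concern.** Suppose RSV-A passes comfortably and one FLU strain narrowly misses. On the planning figures this is the likeliest form of partial failure, because nearly all the type II error sits in the FLU strains. No sentence says outright what is then concluded about RSV-A. The answer has to be inferred: global control at 2.5%, with 2.5% used for every test and no order inside the step, holds only if the first sequence succeeds or fails as a whole. RSV-A is then not formally demonstrated, although it is its own primary objective and was planned at 99.9% power.

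At stake is the formal status of the RSV-A result in that situation. Making the RSV-A claim conditional on FLU brings no gain for FLU or RSV-B. The wording of SAP 2 and 2.1 also leaves the all-or-nothing condition to be deduced.

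**Working it through.** **Inputs** (SAP Section 5, Protocol 9.2): 462 evaluable per group; one-sided alpha 2.5%; margin log10(1.5) = 0.1761; true ratio log10(1.05) = 0.0212; SD of log10 titer 0.45 (RSV-A, RSV-B) and 0.6 (each FLU strain); unadjusted two-sample t-test. The documents give no correlation between strains, so it is varied below.

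**1. Reproduce the plan.**

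- Distance to the margin: 0.1761 − 0.0212 = 0.1549.
- Standard error = SD × √(2/462) = SD × 0.0658, giving 0.0296 (RSV) and 0.0395 (FLU).
- Non-central t power with 922 df: RSV 99.95% (stated 99.9%); each FLU strain 97.50% (stated 97.5%).
- Summed type II error: 2 × 0.054% + 4 × 2.501% = 10.1% (stated about 10.0%).
- Enrolment: 462/0.90 = 513.3, rounded up to 514 per group, as stated.

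**2. Chance that FLU blocks RSV-A.** With independent endpoints:

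- P(all four strains pass) = 0.97499^4 = 0.9037.
- P(first step passes) = 0.99946 × 0.9037 = 90.3%.
- P(RSV-A passes, at least one strain misses) = 0.99946 × (1 − 0.9037) = 9.6%.

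With a common between-strain correlation ρ, P(all four pass) = ∫ φ(u) Φ((c + √ρ·u)/√(1−ρ))^4 du, where c = Φ⁻¹(0.97499). RSV-A is kept independent of FLU:

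| Assumed ρ | RSV-A passes, a FLU strain misses | First step passes |
|---|---|---|
| 0 | 9.6% | 90.3% |
| 0.3 | 8.7% | 91.2% |
| 0.5 | 7.8% | 92.2% |
| 0.7 | 6.5% | 93.4% |
| 1 | 2.5% | 97.4% |

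**3. Sensitivity to the SD.** The planning test is unadjusted, whereas the primary analysis is an ANCOVA with pre-dose titer and age category. If 0.6 is a raw SD and the covariates explain a share R² of variance (an assumption), the residual SD is 0.6 × √(1 − R²). With independent strains:

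| Assumed R² | Power per strain | Any FLU strain misses |
|---|---|---|
| 0 | 97.5% | 9.6% |
| 0.10 | 98.5% | 5.8% |
| 0.25 | 99.5% | 2.0% |
| 0.40 | 99.9% | 0.4% |

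**4. Effect of ordering RSV-A, then FLU, then RSV-B.** Let A, F and B be the events that RSV-A, all four FLU strains and RSV-B meet their limits.

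| Claim | Current rule | Ordered steps |
|---|---|---|
| RSV-A | A and F | A |
| FLU | A and F | A and F |
| RSV-B | A and F and B | A and F and B |

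The FLU and RSV-B rows are the same events, so those probabilities cannot change under any correlation. Only the RSV-A row changes, from 90.3% (ρ = 0) or 92.2% (ρ = 0.5) to 99.9%.

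**5. Type I error.** In the ordered version a false claim requires rejection at the first step that contains a true null. Each step has level 2.5%, the FLU step because all four strains must pass, so family-wise error is at most 2.5%. Simulation of eight null configurations (one million trials each, independent endpoints) gave a maximum of 2.5%. Under the current all-or-nothing rule, if RSV-A and one FLU strain both lie at the margin, a false claim needs both to pass: at most 0.025² = 0.06%. The ordering uses alpha that the current rule leaves unspent.

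**The case against.** The strongest reply is that the plan asks a joint question. The primary estimand in SAP 1.1 is worded as non-inferiority of both vaccines when given together, and requiring RSV-A and all FLU strains at once is a valid test of that. A result with RSV-A shown and FLU not shown would not answer it, and whether a partial claim is wanted is the sponsor's decision. The risk is also disclosed: Protocol Table 16 and SAP Table 2 state a global type II error of about 10%. SAP 4.2.1 has every primary ratio and interval tabulated and plotted, so the RSV-A estimate is reported in any case and only its formal status is affected. All of this stands. It does not explain why RSV-A is listed as a separate primary objective, and the ordered version leaves the joint success probability unchanged.

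The size is also open to challenge. The correlation is unknown, covariate adjustment may shrink the SD, and at a true ratio of 1.0 with independent strains and no covariate gain the chance of any FLU miss is about 2.5%. This stands too, and the loss should be quoted as a range.

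A reader might go further and infer from SAP 2 and 2.1 that RSV-A and FLU may be claimed side by side at 2.5% each. With RSV-A and one strain truly at the margin, family-wise error would then be 1 − 0.975² = 4.9%. The documents do not support that as a description of the plan. Both objectives tables point to SAP 4.2.2 or Protocol 9.4.1.1 for the sequence, Protocol 9.1 says testing is sequential, and SAP 4.8 declares no departure from the protocol. SAP 2 gives the rejection limit for each test and need not repeat the gate. The 4.9% arises only if the governing sequence is ignored.

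**Conclusion.** The current rule, read as all-or-nothing, is valid and controls error at one-sided 2.5%. Its weakness is that it withholds a formal RSV-A claim whenever a FLU strain misses, with nothing gained in return. On the planning inputs the loss runs from 9.6% with independent strains to 2.5% at correlation 1. It is smaller still if covariate adjustment brings the SD below 0.6. That RSV-A is blocked is an inference from the AND rule together with the stated 2.5%, since no sentence says so.

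The gain from reordering is confined to a standalone RSV-A claim. The chance of meeting every primary objective stays at about 90%, so a sponsor interested only in joint success gains no power. Separately, SAP 2.1 is incomplete: a nominal 2.5% per test does not control the global error without the all-or-nothing step and the gate to RSV-B.

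**What to change.** In Protocol 9.4.1.1 and SAP 4.2.2, replace the first sequence by ordered steps, each at one-sided 2.5%:

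1. RSV-A upper limit at most 1.5.
2. Only if step 1 passes: upper limits for all four FLU strains at most 1.5.
3. Only if step 2 passes: RSV-B upper limit at most 1.5.

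State that each objective is demonstrated when its step passes. Reword SAP 2.1 to say that type I error is controlled at 2.5% by this fixed sequence, and add a cross-reference from SAP 2.

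If the sponsor wants joint success only, keep the present first sequence. In that case say explicitly that none of its objectives is claimed when any component misses, and align SAP 2 and 2.1 with that.

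The cost is an amendment to the wording of both documents, made before immunogenicity results by group are seen. It needs no participants, samples, extra alpha or new analyses, and FLU and RSV-B lose no power. Two consequences should be accepted openly: RSV-A shown with FLU not shown becomes a reportable outcome, and the error rate when RSV-A and a FLU strain are both truly at the margin rises from about 0.06% to 2.5%, which is within the stated limit.

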4.2.3. Sensitivity analyses

As for the main analytical approach an ANCOVA model will be performed with the treatment group and age category (age at vaccination: 65-69, 70-79 or ≥ 80 years) as fixed effects, **center as random effect** and the pre-dose \log_{10} -transformed titer as covariate.

In case the model with random effect does not converge we proceed with center as a fixed effect.

4.3. Secondary Endpoints Analyses

4.3.1. Immunogenicity analysis

The primary analysis of secondary immunogenicity endpoints will be based on the PPS for analysis of immunogenicity. If, in any vaccine group, the percentage of vaccinated participants with serological results excluded from the PPS for analysis of immunogenicity is 5% or more, a second analysis based on the ES will be performed to complement the PPS analysis.

4.3.1.1. Between groups assessment

- The asymptotic standardized 95% CI for the difference in seroconversion rate (Control group minus Co-Ad group) will be computed at 1 month after the FLU vaccine (i.e. at Day 31 [Visit 2] for both groups).

Reference criteria for evaluation of non-inferiority:

The upper limit of the 2-sided 95% CI on the group difference (Control group minus Co-Ad group) in seroconversion rate is $\leq 10\%$ for anti-HI antibodies.

The between groups analysis of secondary endpoints presented in this section will be descriptive with the aim to characterize the difference in immunogenicity between groups. These descriptive analysis should be interpreted with caution considering that there is no adjustment for multiplicity for these comparisons.

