6.3.3. Intervention allocation to the participant

An automated Internet-based system, Source data Base for Internet Randomization (SBIR) will be used for randomization and for identification of intervention material. The randomization algorithm will use a minimization procedure accounting for age (65-69, 70-79 or ≥ 80 years) and center. Minimization factors will have equal weight in the minimization algorithm. Refer to Section 4.1.2 for the enrolment rules.

Once a participant identification number is allocated, the randomization system will determine study group and will provide the study intervention number to be used for the first dose. The study intervention number(s) to be used for subsequent dosing will be provided by the same automated Internet-based system (SBIR).

When SBIR is not available, please refer to the SBIR user guide or SPM for specific instructions.

Refer to the SPM for additional information relative to the intervention number allocation.

**6.3.4. Allocation of participants to assay subsets (amended
16 December 2022)**

Not applicable for this study.

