9.4.2. Secondary endpoints

- Method for evaluation of non-inferiority of FLU vaccine in terms of HI seroconversion rate for each of the FLU vaccine strains at 1 month after the FLU vaccine (i.e. at Day 31 for both groups):
 - The 2-sided 95% CI on group difference in seroconversion rate (Control group minus Co-Ad group) will be computed based on the method of Miettinen and Nurminen [[Miettinen](#), 1985].
 - Reference criteria for evaluation of non-inferiority: The upper limit of the 2-sided 95% CI on the group difference (Control group minus Co-Ad group) in seroconversion rate is $\leq 10\%$ for anti-HI antibodies.
- The other secondary endpoints are described in Section 3. Descriptive analyses of demography, immunogenicity and safety will be detailed in the SAP.

Table 19 Definitions of seroconversion rate, seroprotection rate and mean geometric increase

Abbreviation/term	Definition
HI SCR/ seroconversion rate	The percentage of vaccinees who have either a HI pre-dose titer $< 1:10$ and a post-dose titer $\geq 1:40$ or a pre-dose titer $\geq 1:10$ and at least a four-fold increase in post-dose titer.
HI SPR/ seroprotection rate	The percentage of vaccinees with a serum HI titer $\geq 1:40$ that usually is accepted as indicating protection.
MGI/ mean geometric increase	The geometric mean of the within participant ratios of the post-dose titer over the pre-dose titer.

- Additionally, the CBER and CHMP criteria for HI SPR and SCR will be assessed as follows:

CBER's criteria:

- The lower limit (LL) of the 95% CI for SCR should be $\geq 30\%$ in participants ≥ 65 YOA.
- The LL of the 95% CI for SPR should be $\geq 60\%$ in participants ≥ 65 YOA.

CHMP's criteria:

At least one of the 3 following criteria should be met:

- the point estimates of SPR $>60\%$, SCR $>30\%$, and MGI >2.0 for elderly ≥ 60 YOA for each of the antigen strains.

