4. STATISTICAL ANALYSES

4.1. General Considerations

4.1.1. General Methodology

95% CI for proportion will be based on exact Clopper-Pearson confidence interval [[Clopper](#), 1934].

95% CI for group difference in proportion will be based on Miettinen and Nurminen confidence interval [[Miettinen](#), 1985].

The group adjusted GMT ratio will be based on a back transformation of group contrast in an ANCOVA model applied to the logarithm- transformed titers.

Primary Analysis: The ANCOVA model will include the treatment group and age category (age at vaccination: 65-69, 70-79 or ≥ 80 years) as fixed effects and the pre-dose log-10 titer as regressors.

Sensitivity Analysis: The ANCOVA model will include the treatment group and age category (age at vaccination: 65-69, 70-79 or ≥ 80 years) as fixed effects, center as the random effect and the pre-dose log-10 titer as regressors.

95% CI for GMT will be based on a back transformation of student CI for the mean of log-transformation.

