Table 3 Evaluation of non-inferiority in terms of HI antibody SCR when the FLU vaccine is co-administered with the RSVPreF3 OA investigational vaccine as compared to FLU when administered alone assuming 462 participants are available in each group for a range of plausible SCRs.

N evaluable participants per group	Threshold	Plausible rates in Control group**	Type II error	Nominal power
FLU vaccine: Non-inferiority* in terms of SCR				
462	10%	70%	8.7%	91.3%
462	10%	50%	13.9%	86.1%
462	10%	35%	11.0%	89.0%
462	10%	25%	6.1%	93.9%

SCR: Seroconversion Rate.

*Pass 2019 alpha = 2.5%, for SCR – Non-inferiority: Proportions – Two independent Proportions – Non-Inferiority Tests for the Difference Between Two Proportions based on Miettinen and Nurminen method

** SCR observed in the Control group in Zoster-004 study range from 35.3% to 60.9%.

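### The seroconversion difference is planned without age stratification although allocation is minimised on age: the interval is valid but slightly conservative, and a small gain in precision is available at little cost.

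*SAP*

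**What the plan says.** - **Allocation.** Protocol 6.3.3: "The randomization algorithm will use a minimization procedure accounting for age" (65-69, 70-79, 80 or more) and center, with equal weight.
- **Primary model.** SAP 4.2.2 and protocol 9.4.1 fit an ANCOVA to the log titers with treatment group, age category and pre-dose titer. Center enters only the sensitivity model (SAP 4.2.3).
- **Seroconversion difference.** Protocol 9.4.2 says that the interval "will be computed based on the method of Miettinen and Nurminen". SAP 4.1.1 has the general rule: "95% CI for group difference in proportion will be based on Miettinen and Nurminen confidence interval". SAP 4.3.1.1 plans "The asymptotic standardized 95% CI for the difference in seroconversion rate", Control minus Co-Ad at Day 31, with the criterion that the upper limit of the difference "in seroconversion rate is $\leq 10\%$ for anti-HI antibodies". None of these places names strata or covariates, and no age-adjusted between-group version is planned.
- **Status.** SAP 4.3.1.1 calls these between-group comparisons descriptive and without multiplicity adjustment. The confirmatory sequence in SAP 4.2.2 contains only GMT ratios.
- **Power.** SAP section 5, Table 3 gives 91.3, 86.1, 89.0 and 93.9% at control rates of 70, 50, 35 and 25%, from "Non-Inferiority Tests for the Difference Between Two Proportions based on Miettinen and Nurminen method".
- **Age.** SAP 4.3.1.2 tabulates seroconversion by age within each group. SAP 6.2.3.2 takes the analysis age categories from SBIR.

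**The concern.** When a factor that predicts the outcome is balanced between groups by design, differences between its levels add almost nothing to the true error of the group difference. The unstratified variance still counts them, so the interval comes out wider than it needs to be. The plan adjusts the Day 31 HI titers for age in the GMT analysis but not the seroconversion status derived from those same titers, and it gives no reason for the difference.

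What is at stake is precision in the least-powered comparison with a limit of its own. Stated power per strain is 86.1 to 93.9% for seroconversion, against 97.5% for each HI GMT ratio and 99.9% for the RSV GMT ratios.

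**Working it through.** **Inputs from the documents.** n = 462 evaluable per group, 1:1 allocation, margin 0.10, one-sided alpha 2.5% (z = 1.96). A true difference of 0 is inferred, because it reproduces Table 3.

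**Assumed inputs.** The documents give no seroconversion rate by age. Protocol 4.1.2 fixes about 25/40/10% of participants by age category and leaves 25% free; I use weights w = 0.33/0.50/0.17, close to an even spread of the free quarter.

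**Step 1: reproduce the plan's figures.** With SE = sqrt(2p(1-p)/n) and power = Phi(0.10/SE - 1.96):

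| Control rate | SE | Power | SAP Table 3 |
|---|---|---|---|
| 70% | 0.03015 | 91.3% | 91.3% |
| 50% | 0.03290 | 86.0% | 86.1% |
| 35% | 0.03138 | 89.0% | 89.0% |
| 25% | 0.02849 | 93.9% | 93.9% |

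Exact binomial enumeration of the unstratified Miettinen-Nurminen test gives 91.3, 86.1, 89.1 and 94.0%. The stated power is therefore that of an analysis without age.

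**Step 2: split the variance by age.** Let p be the weighted mean rate.
- Marginal variance: V_m = p(1-p), which the unstratified interval uses.
- Within-age variance: V_w = sum of w_k p_k(1-p_k), which the stratified interval uses.
- V_m - V_w is the between-age part.
- SE_m = sqrt(2V_m/n) and SE_w = sqrt(2V_w/n).

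For 60/50/40%:
- p = 0.33(0.60) + 0.50(0.50) + 0.17(0.40) = 0.516.
- V_m = 0.516 × 0.484 = 0.24974.
- V_w = 0.33(0.24) + 0.50(0.25) + 0.17(0.24) = 0.24500, which is 1.9% lower.
- SE_m = 0.03288 and SE_w = 0.03257.
- Interval half-width: 6.44 points unstratified, 6.38 stratified.

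**Step 3: power with age balanced.** Under balance both estimates of the difference have true standard error SE_w. The unstratified test differs only in using SE_m for its critical distance.
- Unstratified: Phi((0.10 - 1.96 SE_m)/SE_w).
- Stratified: Phi(0.10/SE_w - 1.96).

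For 60/50/40%:
- Unstratified: (0.10 - 1.96 × 0.03288)/0.03257 = 1.092, so 86.3%.
- Stratified: 0.10/0.03257 - 1.96 = 1.111, so 86.7%.

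| Assumed rates by age | Variance reduction | Unstratified, age balanced | Stratified | Gain (points) |
|---|---|---|---|---|
| no age effect (50% throughout) | 0 | 86.0% | 86.0% | 0 |
| 55/50/45% | 0.5% | 86.1% | 86.2% | 0.1 |
| 60/50/40% | 1.9% | 86.3% | 86.7% | 0.4 |
| 70/50/30% | 7.6% | 87.1% | 88.7% | 1.6 |

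**Step 4: sensitivity to the age mix.** Weights of 33/48/18% with an overall rate of 50% give 86.2 to 86.7% for a 10-point gap between adjacent categories, and 87.0 to 88.6% for a 20-point gap. The picture is the same.

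**The case against.** The strongest reply is that nothing here is an error. The unstratified interval is valid, is named in both documents, matches the power calculation and errs on the cautious side for non-inferiority. The comparison is descriptive, so no confirmatory conclusion or alpha depends on it. Age is not ignored either, since seroconversion is tabulated by age within groups. All of this stands, and it limits the point to an optional improvement. The within-group tables do not, however, sharpen the between-group interval that is read against the 10% limit.

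Stronger readings that a reader might infer are not supported:
- **A larger gain.** Setting the nominal power of Step 1 against stratified power suggests gains of about 0.2, 0.7 and 2.6 points. That treats age as unbalanced for one analysis and balanced for the other. Under balance the unstratified test already does better than its nominal power, so the gains are those in the table.
- **A power shortfall.** The stated powers reproduce and need no correction.
- **Full agreement with the allocation and the primary model.** Age stratification covers only one of the two minimisation factors, because center stays out. It also omits the pre-dose titer, which is in the ANCOVA.

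Two practical objections also stand. A stratified estimate is not defined until its weights are stated. And the stratum aged 80 or more may hold only about 10% of participants, roughly 46 of 462 per group, although that is workable with three strata.

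**Conclusion.** The point holds as a minor gain in efficiency. The planned seroconversion interval is valid, and is slightly conservative if seroconversion varies with age. With control seroconversion near 50%, 462 per group and age balanced by minimisation, stratifying adds about 0.1 to 0.4 point of power per strain for gaps of 5 to 10 points between adjacent age categories, and about 1.6 points for a 20-point gap. It adds nothing if there is no age effect. The gradients are assumptions: SAP Table 3 cites only overall control rates of 35.3 to 60.9% from a previous study. No primary conclusion is affected.

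**What to change.** In SAP 4.3.1.1, with matching wording in protocol 9.4.2, specify for each strain:
- a Miettinen-Nurminen interval for the seroconversion difference stratified by SBIR age category;
- the stratum weights, for example Mantel-Haenszel or sample-size weights;
- the unstratified interval, on which the power table rests, reported alongside;
- which of the two is read against the 10% limit, so that the choice is made before results are seen.

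The cost is a sentence or two in the SAP, a clause in the protocol and a small addition to the analysis program. The stratification variable already exists under SAP 6.2.3.2. If the protocol is not reopened, the stratified interval can be added to the SAP as supportive, with SAP 4.8 updated, since it now states that nothing departs from the protocol. Sample size and stated power stay as they are.
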